4.1. Intent-to-treat

The primary analysis of the between subject endpoints will adhere to the intent-to-treat principle. Under this principle, all subjects randomized to either the VLNC or NNC arm will be included in the analysis in the group to which they were randomized regardless of protocol violations and compliance to treatment assignment.

4.2. Per-Protocol

A secondary per-protocol analysis will include only participants who complete all 5 sessions.

5. Trial Endpoints

5.1. Primary Endpoint

- Number of cigarette puffs taken: Among the 5 sessions, the first session is always cigarettes only, no e-cigs, and each of the 10 choices is between taking 2 cigarette puffs or abstaining from smoking. At each session where e-cigs are available (i.e., Sessions 2-5), each of the 10 choices is between taking 2 cigarette puffs, 2 e-cig puffs, or abstaining from both. The maximum number of cigarette puffs taken will be 20 for each of the five sessions.

5.2. Secondary Endpoints

- Number of e-cig puffs taken (0 to 20)
- CO boost

5.3. Exploratory Endpoints

- Number of choices for cigarette puffs (0 to 10)
- Number of choices for e-cig puffs (0 to 10)
- Number of choices to abstain from puffing (0 to 10)
- Measures of compliance: drop-out rate
- Measures of discomfort/dysfunction: MNWS, QSU, PANAS
- Measures of cigarette characteristics: CES, Cigarette Purchase Task indices
- Measures of perceived risk: Perceived Health Risk Scale
- Measures of cardiovascular function: heart rate, blood pressure
- Biomarkers: TNE, NMR, Cotinine, CO

5.4. Safety Endpoints

- Adverse Events (AEs)
- Serious adverse events (SAEs)

6. Statistical Analysis

6.1. General Approach

The primary objective of this trial is to compare the effects of VLNC and NNC cigarettes, and of the availability and characteristics of e-cigs, on preference for cigarette puffs, e-cig puffs, or puffing abstinence. The within subject factors (between sessions) will allow for the comparison of two levels of nicotine concentration in e-cigs and two categories of e-cig flavors in a 2 x 2 factorial design. Statistical analyses will be performed using SAS or R. All analyses will be completed using the intent-to-treat principle unless otherwise noted. Methods for handling missing data will be specified below. All statistical tests will be two-tailed and a p-value less than 0.05 will be considered significant for all endpoints.

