Project 3 will use laboratory methods with adolescent daily smokers to examine the effects of nicotine content in cigarettes on the reinforcing value and positive subjective effects of cigarette smoking. We will examine how concurrent availability of vaping devices and key vaping characteristics (nicotine concentration and flavors) influence preference to use these products and subjective responses (e.g., liking, satisfaction, sensory effects, outcome expectancies, and perceptions of harm).

Nicotine, tobacco, and adolescents

Cigarette smoking is one of the leading causes of preventable death worldwide (WHO, 2013). Smokers on average lose ten years of life expectancy compared to nonsmokers (Thun et al., 2013). Adolescence is a critical developmental period for tobacco initiation and progression to regular use and dependence, and the vast majority of adult cigarette smokers began smoking in adolescence. Because early age of smoking initiation is associated with greater lifetime exposure to tobacco smoke, those who begin smoking during adolescence are at greater risk for developing tobacco dependence and smoking-related disease and death compared with adult initiators (Jha et al., 2013; Kendler et al., 2013; Marshall et al., 2006). In addition to these risks over the life course, prolonged exposure to nicotine during adolescence is harmful for brain development and can result in prefrontal cortex deficits and changes in behavioral risk factors such as impulsivity that may be permanent (Goriounova et al., 2012; Musso et al., 2007). Comprehensive tobacco control policies that reduce risk of tobacco use in adolescence are critically needed to minimize death, disease, and other harms caused by tobacco use.

Reducing nicotine to reduce the addictiveness of combusted tobacco

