Table of Contents

1.	3
2.	3
3.	3
3.1.	4
3.2.	4
4.	5
4.1.	5
4.2.	Per-protocol.....
	5
5.	5
5.1.	5
5.2.	5
5.3.	Error! Bookmark not defined.
5.4.	Safety Endpoints.....
	6
6.	6
6.1.	6
6.2.	6
6.3.	6
6.3.1.	6
6.3.2.	7
6.4.	7
6.5.	7
6.6.	8
6.7.	8
6.8.	8

1. Introduction

This document will serve as the Statistical Analysis Plan for CENIC 2 Project 3, entitled “Effects of Very Low Nicotine Content Cigarettes and E-cigarette Characteristics on Smoking in Adolescents. This document describes the planned statistical analysis for evaluating the effects of cigarette nicotine content, electronic cigarette (e-cig) nicotine concentration and e-cig flavor on combustible cigarette smoking in adolescents within a laboratory setting. Details for the proposed analysis of the primary and secondary endpoints are provided.

2. Trial Objectives

This study of adolescent smokers will examine the effects of cigarette nicotine content and e-cig availability, nicotine content and flavoring using a laboratory-based preference task in which the nicotine content of cigarettes, the concurrent availability of e-cigs, and the characteristics of e-cigs (nicotine concentration and flavors), are manipulated. The **primary aim** is to test the effects of nicotine content in cigarettes, and nicotine concentration and flavors in e-cigs on choices to smoke a combustible cigarette, vape an e-cig, or abstain from both, in a sample of adolescent smokers. The **secondary aim** will test the effects of nicotine content in cigarettes, nicotine concentration in e-cigs, and e-cig flavors on subjective effects. Lastly, the **exploratory aim** explores the extent to which participant factors (gender, CPD and dependence) influence the effects of nicotine content in cigarettes, nicotine concentration in e-cigs, and flavors in e-cigs.

3. Trial Design

This is a randomized, single site, double-blind, $2 \times 2 \times 2$ laboratory-based study conducted on 120 adolescent daily smokers. These smokers will be assigned to receive either normal nicotine content (NNC) or very low nicotine content (VLNC) cigarettes. The first laboratory session will be a control session with only cigarettes, and no e-cigs, available. This will be followed by the 4 e-cig laboratory sessions with cigarette (tobacco; tobacco menthol) flavored e-liquid or non-cigarette (e.g., fruit; mint; vanilla; candy) flavored e-liquid and two levels of nicotine concentration as shown in the table below.

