3.2. Sample Size

Very little has been reported in the literature on the effect of VLNC cigarettes or the dual use of e-cigarettes on adolescent smokers. To determine a reasonable effect size (ES=mean diff/common SD) for sample size calculations, we considered several recent studies investigating alternatives to usual brand cigarettes in adolescents and young adults. In the first project of the CENIC 1 center grant, cigarettes per day (CPD) at weeks 2 and 6 were recorded for adult smokers using cigarettes with the same level of nicotine planned for our current project (15.8 mg/g vs 0.4 mg/g). (Donny et al., 2015) Selecting out the youngest participants (18-24 years of age), the comparison between these two nicotine groups resulted in an ES of 0.76 at 2 weeks and 0.85 at 6 weeks. A recent study of adolescent smokers (Cassidy et al., 2015) used a very similar design as the current proposal. Participants made a series of 20 choices between puffs of their usual brand cigarettes or money, where the amount of money varied over three sessions assigned to each subject in random order (\$0.00, \$0.10, \$0.50). The ES for the comparison between 10 and 50 cents was 0.73. Therefore, based on these previous studies, we determined that 60 subjects per cigarette group would allow for the detection of an ES of 0.60 or higher with minimum statistical power of 90% for a two-sided, two-sample test where the significance level is 0.05. For the within subject comparisons defined by the 2 factors for the e-cig characteristics, an ES of 0.5 or more for the two main effects would have at least 97% power in a repeated measures analysis if the sample size is 60 per cigarette group with a significance level of 0.05. Study enrollment will continue until the number of subjects completing all 5 sessions reaches 60 in each group (120 total). Sample size and power calculations were carried out using PASS 13 (NCSS, LLC. Kaysville, Utah, 2014).

4. Study Populations

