6.3.1. Primary Analysis

Descriptive statistics will summarize the number of cigarette puffs by cigarette group and by session. Results will be presented in tabular and graphical format. The primary statistical model will be a linear mixed model (2) carried out according to the 2 x 2 x 2 design, where the between-subject factor is NNC or VLNC cigarettes and the two within-subject factors relate to e-cig flavor (cigarette or non-cigarette flavors) and nicotine content (very low or moderate). The session where no e-cigs are included will be analyzed separately by comparing the normal and reduced nicotine cigarettes groups using linear regression adjusting for baseline CPD from TLFB to improve precision. Sandwich standard

errors will be used to account for potential heteroscedasticity. Data from the four sessions where e-cigs are available will be analyzed using a linear mixed model to account for potential correlation between repeated measures on an individual. The mixed model for the balanced factorial design will allow for the evaluation of the three main effects and their interactions. The major concern for this approach is the occurrence of non-constant variance for the number of cigarette puffs. Therefore, sensitivity analysis will be performed to evaluate the robustness of our assumptions. A generalized estimating equation (GEE) model uses sandwich estimators and thus is less affected by unequal variances, however, is more negatively impacted by the occurrence of missing observations. Additionally, a negative binomial regression approach will check if modeling the number of puffs as count variables provides a better fit to the data. The first mixed model will assume that participant characteristics are balanced between groups due to randomization and include only the three main effects and their interactions along with the stratification variables (gender, menthol status, and CPD [continuous, from the BL TLFB]) and the number of cigarette puffs from session 1 to increase precision.

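### The SAP's stated primary objective includes e-cig availability, but no planned contrast estimates its effect or how that effect differs between VLNC and NNC

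*Combined protocol and SAP*

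**What the plan says.** Three places name availability separately from the e-cig characteristics:

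- SAP 6.1: "The primary objective of this trial is to compare the effects of VLNC and NNC cigarettes, and of the availability and characteristics of e-cigs".
- SAP 2, on the preference task: "the concurrent availability of e-cigs, and the characteristics of e-cigs (nicotine concentration and flavors), are manipulated".
- Protocol, Objective: "We will examine how concurrent availability of vaping devices and key vaping characteristics (nicotine concentration and flavors) influence preference to use these products".

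The labelled primary aim in SAP 2 is narrower. It "is to test the effects of nicotine content in cigarettes, and nicotine concentration and flavors in e-cigs on choices to smoke" a cigarette, vape or abstain. The primary aim under Statistical Approach in the protocol lists the same three factors. The power text (SAP 3.2, matched by the protocol's Power Analysis) covers the two-group cigarette comparison and then speaks only "For the within subject comparisons defined by the 2 factors for the e-cig characteristics".

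SAP 6.3.1 sets out the analysis:

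- "Descriptive statistics will summarize the number of cigarette puffs by cigarette group and by session".
- "The session where no e-cigs are included will be analyzed separately by comparing the normal and reduced nicotine cigarettes groups", by linear regression adjusted for baseline CPD with sandwich standard errors.
- "Data from the four sessions where e-cigs are available will be analyzed using a linear mixed model", with three main effects, their interactions, the stratification variables, and Session 1 cigarette puffs as a covariate added for precision.

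**The concern.** Availability varies only between Session 1 (no e-cig) and Sessions 2-5 (e-cig present). An analysis confined to one side of that split cannot estimate its effect, and both planned inferential analyses of the primary endpoint are so confined.

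Someone who follows the SAP exactly will have raw means by group and session. They will have no planned interval or test for whether e-cig availability changed smoking, or whether it did so differently under VLNC. SAP 6.1 makes this part of the primary objective, and the protocol's Overall Study Design also asks how e-cig availability alters the effect of VLNC. Without a named contrast, any formal statement on availability would rest on an analysis chosen later.

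**Working it through.** **1. The plan's own power figures.** Inputs from SAP 3.2: 60 per group, two-sided 0.05, effect sizes 0.60 (between) and 0.5 (within).
- Between: 0.60 × √(60/2) = 3.286. Normal power is Φ(3.286 − 1.960) = 90.8%, and 90.3% by noncentral t. The stated 90% reproduces.
- Within: 0.5 × √60 = 3.873. Normal power is Φ(3.873 − 1.960) = 97.2%, and 96.8% by noncentral t. The stated 97% reproduces to rounding.

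Neither figure concerns availability.

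**2. Where Session 1 is used.**

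| Place | Use of Session 1 | Estimates availability? |
|---|---|---|
| SAP 6.3.1, separate regression | outcome, VLNC vs NNC | No: no e-cig for anyone |
| SAP 6.3.1, mixed model | covariate; outcomes are Sessions 2-5 | No: e-cig available in every row |
| SAP 6.3.1, summaries | means by group and session | Descriptively only |
| SAP 6.4, CO boost | measured in all five sessions, same 2 x 2 x 2 model | No such term |
| SAP 6.5, exploratory | generic mixed model for repeated measures | No contrast named |

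The number of cigarette choices (SAP 5.3) is puffs divided by 2, so the SAP 6.5 model could carry the primary outcome, rescaled, over all five sessions. It still names no availability term.

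**3. Precision of the missing between-arm contrast.** The documents give no within-person correlations, so those below are assumptions. Let D = mean(Sessions 2-5) − Session 1. The SD is 1 in every session, r1 is the correlation of Session 1 with each later session, and r2 is the correlation among later sessions.

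Var(D) = 1 + (1 + 3·r2)/4 − 2·r1

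The 95% half-width for the between-arm difference in D is 1.96 × √(2·Var(D)/60). Power is for a 0.3 SD difference (t, 118 df).

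| r1 | r2 | Var(D) | Half-width (SD) | Power |
|---|---|---|---|---|
| 0.3 | 0.3 | 0.875 | 0.335 | 41% |
| 0.5 | 0.5 | 0.625 | 0.283 | 54% |
| 0.7 | 0.7 | 0.375 | 0.219 | 76% |
| 0.3 | 0.7 | 1.175 | 0.388 | 32% |

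Within one arm the half-width is smaller by √2: 0.24, 0.20, 0.15 and 0.27 SD. Unequal SDs can widen the range. If the later SD is 1.25 times that of Session 1, with r1 = 0.3 and r2 = 0.7, Var(D) = 1 + 1.5625 × 3.1/4 − 2 × 1.25 × 0.3 = 1.461. The between-arm half-width is then 0.43 and power is 27%.

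**4. Scale.** The outcome is bounded at 0 to 20 puffs (SAP 5.1). Assume Session 1 means of 16 (NNC) and 12 (VLNC).
- The same 40% reduction in both arms (to 9.6 and 7.2) gives an additive contrast of (7.2 − 12) − (9.6 − 16) = +1.6 puffs.
- The same odds ratio of 0.37 in both arms (to 11.91 and 7.11) gives (7.11 − 12) − (11.91 − 16) = −0.80 puffs.

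A common effect on one scale can therefore appear as an interaction of either sign in puffs. For an SD between 6 and 4 puffs, 1.6 puffs is 0.27 to 0.40 SD.

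**The case against.** The best defence is that the labelled aims, the power sections and the 2 x 2 x 2 model agree with one another, so availability is loose framing around a coherent plan. The agreement is real. It does not remove the conflict, because SAP 6.1 uses the term primary objective and no section says which statement governs.

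Second, the protocol deliberately treats Session 1 as the baseline condition and places it first to avoid carryover from e-cigs. That explains the order and the covariate, but not the absence of a comparison with that baseline.

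Third, SAP 6.5 could stretch to a five-session model of cigarette choices. This narrows the gap to an unnamed contrast in an exploratory analysis.

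Fourth, the protocol mentions a marginal structural model. It concerns e-cig use as a mediator, is only to be considered, and does not appear in the SAP.

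Fifth, the contrast would be order-confounded, scale-dependent and possibly imprecise. All of that stands. It argues for stating the limits or dropping the objective, not for leaving an objective without an analysis.

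A reader might infer more: that the plan offers the Session 1-adjusted arm coefficient as its availability estimate and so would mislead. The documents do not support that. SAP 6.3.1 gives precision as the only reason for the covariate. The coefficient equals the arm difference in Sessions 2-5 minus a slope times the arm difference in Session 1, so it matches the availability interaction only if that slope is 1. The plan never claims otherwise.

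**Conclusion.** The mismatch holds on the text alone. Availability is in the objectives of SAP 2, SAP 6.1 and the protocol, and no planned inferential contrast estimates it or its VLNC-NNC difference. It should be resolved, at moderate priority.

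A reader might also infer that the primary analysis is invalid or underpowered. That does not follow: the factorial model tests the three labelled factors, and both stated power figures reproduce.

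The missing between-arm contrast would carry a 95% half-width of about 0.22 to 0.39 SD. This assumes 60 per arm, correlations of 0.3 to 0.7 and equal SDs, none of which except the sample size comes from the documents.

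**What to change.** Choose one option, and label either one post hoc if data are already unblinded.

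**Option 1: add the analysis.** In SAP 6.3.1, add a supporting (not primary) mixed model with all five sessions as outcomes, by cigarette group. Include the stratification factors, leave out the Session 1 puffs covariate, and use a covariance that lets Session 1 differ from the others. Report with confidence intervals:

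1. the mean of Sessions 2-5 minus Session 1 within each arm;
2. the between-arm difference in (1), with a ratio-scale version beside it, for example a log-link GEE. SAP 6.3.1 plans GEE but names no log link, so this would be a new specification.

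State these limits:
- (1) is confounded with Session 1 always being first, with e-cig sampling puffs, and with time since the sampled cigarette. One 15-minute delay follows it in Session 1; in Sessions 2-5, two delays and the e-cig sampling follow it.
- (2) assumes those effects are equal in both arms, is scale-dependent, and may be imprecise.

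**Option 2: change the wording.** Remove availability from the protocol Objective, SAP 2 and SAP 6.1 together, and check the Overall Study Design text for consistency. Changing only the SAP would leave the mismatch in place.

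**Separately, a small point.** Add gender and menthol status to the Session 1 regression. Both are randomisation strata (SAP 3.1) and are already in the mixed model, but that regression adjusts only for CPD.

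**Cost.** Option 1 is one extra model on data already collected, with disclosed order confounding and limited precision. Option 2 is wording only. Neither changes procedures, sample size or the primary model.

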Demographics and baseline data will be compared between the groups randomized to NNC or VLNC cigarettes using t-tests and chi-square tests. The endpoints of interest are the number of puffs from cigarettes, the number of puffs from e-cigs, and the number of choices to abstain from both cigarettes and e-cigs. Descriptive statistics will summarize the data by cigarette group and by session. Results will be presented in tabular and graphical format.

The **primary aim** is to examine the effects of cigarette nicotine content, e-cig nicotine concentration and e-cig flavor on choices to smoke. The primary outcome measure is the number of cigarette puffs, and the secondary outcomes are the number of e-cig puffs, and CO boost.

The **secondary aim** is to examine the effects of these factors on product appeal and sensory effects (Cigarette/E-Cig Evaluation Scale), perceived health risks (Perceived Health Risks Assessment), and pre- to post-use changes in craving (QSU), withdrawal symptoms (MNWS), and affect (PANAS). The primary statistical model to test both aims will be a linear mixed model carried out according to the $2 \times 2 \times 2$ design, where the between-subject factor is NNC or VLNC cigarettes and the two within-subject factors relate to e-cig flavor (cigarette or non-cigarette) and nicotine concentration (very low or moderate). The session where no e-cigs are included will be analyzed separately by comparing choices for NNC vs. VLNC cigarettes using a two sample t-test with unequal variances. The mixed model for the balanced factorial design will allow for the evaluation of the three main effects and their interactions. The major concern for this

approach is the occurrence of non-constant variance for the number of puffs of each product or the number of times abstaining as the dependent variables. Therefore, sensitivity analyses will be performed to evaluate the robustness of our assumptions. A generalized estimating equation (GEE) model uses sandwich estimators and thus is less affected by unequal variances, however, it is more negatively impacted by the occurrence of missing observations. Additionally, a negative binomial regression approach will check if modeling the number of puffs as a count variable provides a better fit to the data. The first mixed model will assume that participant characteristics are balanced between groups due to randomization and include only the three main effects and their interactions.

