6.4. Secondary Endpoint Analysis

Secondary endpoints will be summarized by cigarette group and lab session using the mean and standard deviation. Number of puffs of e-cigs taken are measured in sessions 2 to 5, where e-cigs are available. CO boost (i.e., post-choice CO minus pre-choice CO) is measured at every session (1 to 5). The analysis of the secondary endpoints will be a linear mixed model following the same 2 x 2 x 2 factorial design outlined in section 6.3.1. First with only main effects and interaction terms along with the stratification and the baseline values to increase precision, and then a second model adding in any important baseline characteristics as potential moderators of study outcomes.

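### SAP 6.1 calls any p below 0.05 significant for every endpoint, with no multiplicity control or descriptive label for the secondary and exploratory results, and the subjective measures have two different tiers

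*Combined protocol and SAP*

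**What the plan says.** SAP 6.1 sets one rule for the whole analysis: "All statistical tests will be two-tailed" and "a p-value less than 0.05 will be considered significant for all endpoints". I found no multiplicity adjustment, hierarchy or descriptive-only statement in the SAP or the protocol. The SAP does opt out of formal testing where it wants to: SAP 6.6 plans no formal comparison of adverse event rates. SAP 6.4 and 6.5 contain nothing similar.

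SAP 5.2 lists two secondary endpoints, e-cig puffs and CO boost. SAP 6.4 analyses each with the factorial model of SAP 6.3.1, which estimates three main effects and their interactions. It then fits a second model, "adding in any important baseline characteristics as potential moderators of study outcomes".

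On the subjective measures, the SAP 2 secondary aim "will test the effects of nicotine content in cigarettes, nicotine concentration in e-cigs, and e-cig flavors on subjective effects". The protocol's Statistical Approach names the measures for that aim (CES, Perceived Health Risks, QSU, MNWS, PANAS) and says "The primary statistical model to test both aims will be a linear mixed model". SAP 5.3, however, lists them as exploratory, for instance "Measures of discomfort/dysfunction: MNWS, QSU, PANAS", and the protocol's Outcome Variables section does the same.

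**The concern.** A plan may leave secondary and exploratory endpoints unadjusted, provided it says that their p-values are not confirmatory. This plan does not say so, and SAP 6.1 applies the word significant to all of them. Followed as written, it would allow an isolated effect of e-cig flavour or nicotine concentration on e-cig puffs, or on appeal or perceived risk, to be reported as significant with no note on how many tests were run. The protocol's section on expected benefits says the information may ultimately help the FDA decide how to regulate tobacco products, so a chance finding could be given more weight than it can bear.

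The tier mismatch makes this worse for the subjective measures. A reader who wants to discount exploratory p-values cannot tell whether a CES or QSU result answers a stated secondary aim or is exploratory.

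**Working it through.** **The plan's own figure.** The documents give no family-wise error rate. The related stated figure is power: "minimum statistical power of 90% for a two-sided, two-sample test where the significance level is 0.05", for an effect size of 0.60 with 60 per group. The noncentrality is 0.60 x √(60/2) = 3.286. The normal approximation gives Φ(3.286 − 1.960) = 0.908, and the noncentral t with 118 df gives 0.903. The figure reproduces, but it is for one comparison at 0.05 and makes no allowance for several.

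**Inputs.**
- Threshold: 0.05, two-sided, all endpoints (SAP 6.1).
- Secondary endpoints: 2 (SAP 5.2).
- Effects per model: 3 main effects + 3 two-way interactions + 1 three-way interaction = 7 (SAP 6.3.1, applied through SAP 6.4).
- Tests: 2 x 7 = 14, or 2 x 3 = 6 if only main effects count.
- Interim looks: none (SAP 6.8).
- Correlation between the two endpoints' test statistics for the same effect: not given in the documents, so varied from 0 to 0.95. Its sign does not matter for two-sided tests.

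**Formula.** Assume all nulls are true and treat the seven effects as independent, as in a balanced orthogonal design. Let q be the probability that both endpoints are non-significant for one effect. Then P(at least one) = 1 − q^m, where m is the number of effects. At correlation 0, q = 0.95² = 0.9025. At 0.95, the bivariate normal gives q = 0.9354.

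| Correlation | q | One test per endpoint (2 tests) | Main effects only (6 tests) | All effects (14 tests) |
|---|---|---|---|---|
| 0 | 0.9025 | 0.098 | 0.265 | 0.512 |
| 0.5 | 0.9093 | 0.091 | 0.248 | 0.486 |
| 0.8 | 0.9219 | 0.078 | 0.216 | 0.434 |
| 0.95 | 0.9354 | 0.065 | 0.181 | 0.373 |

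For example, with all effects, 1 − 0.9025^7 = 0.512 and 1 − 0.9354^7 = 0.373. The expected number of false positives among 14 tests is 14 x 0.05 = 0.70 at any correlation.

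**Tier of the subjective measures.**

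| Place | Status |
|---|---|
| SAP 2 | Secondary aim; subjective effects, no scale named |
| Protocol, Statistical Approach | Secondary aim; five measures named |
| Protocol, Outcome Variables | Exploratory |
| SAP 5.3 and 6.5 | Exploratory |

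The two endpoint lists agree with each other. The two statements of the aim do not agree with them.

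**The case against.** The strongest reply is that SAP 6.1 only sets a nominal threshold. The primary, secondary and exploratory tiers remain in SAP 5.1 to 5.3, leaving lower tiers unadjusted is common practice, and the plan announces no confirmatory secondary claim. Much of this stands: the missing adjustment is not an error in itself. It does not rescue the wording, because no sentence says that the tiers limit how a p-value below 0.05 may be described.

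A reader might infer several stronger points that the documents do not support:

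- **That a chance secondary claim is as likely as not.** This is true only near the top of the range, with all seven effects per endpoint treated as claims and the endpoints close to independent. It also needs every null to be true. That is a strict assumption here: each trial is a choice between cigarette, e-cig and abstaining, so e-cig puffs partly mirror cigarette puffs, and SAP 3.2 sizes the study for effects of 0.5 to 0.6 SD.
- **That there are 15 secondary tests.** CO boost is measured at Session 1, but SAP 6.4 does not expressly plan a separate Session 1 test of it. That value may serve as the baseline covariate.
- **That the five subjective measures add 35 formal secondary tests.** SAP 2 names no scale, and both endpoint lists call these measures exploratory.
- **That the SAP 6.4 moderators fall outside the exploratory label.** The protocol's Statistical Approach puts moderator analyses under the Exploratory Aim, with gender, baseline CPD and dependence given as an open list. SAP 6.4 only fails to repeat the label.

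**Conclusion.** The point holds as a defect of wording and status. SAP 6.1 authorises the word significant for every endpoint, with neither error control nor a descriptive label below the primary endpoint. For the two secondary endpoints, the chance of at least one such result under the complete null is about 0.37 to 0.51 for 14 tests, 0.18 to 0.26 for main effects only, and about 0.10 for one test per endpoint (0.065 if the endpoints are almost perfectly correlated).

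These figures are calculated here, not taken from the documents. They assume that all nulls are true, that factorial effects are independent within an endpoint, and that the correlation between endpoints lies between 0 and 0.95. The second models with baseline characteristics and the per-protocol analysis are not counted.

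The tier mismatch for the subjective measures is real but narrow: the statements of the aim differ from two endpoint lists that agree. Correcting both changes what the trial may conclude from its secondary results. It does not affect the design, the sample size or the primary model.

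**What to change.** 1. In SAP 6.1, remove the clause that extends significance to all endpoints. State that secondary and exploratory results are reported as estimates with 95% confidence intervals and nominal p-values, which are unadjusted for multiplicity and do not support confirmatory claims.
2. In SAP 2 and the protocol's Statistical Approach, state that the subjective measures are exploratory, in line with the protocol's Outcome Variables section and SAP 5.3.
3. In SAP 6.4, label the moderator analyses exploratory, as the protocol does.
4. Do not make secondary testing conditional on the primary endpoint unless one deciding primary test and one main effect per secondary endpoint are named first. The primary endpoint has seven factorial effects plus a Session 1 comparison. If any of these eight could open the gate, it would open by chance with probability 1 − 0.95^8 = 0.34 under independence.

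The cost is a few sentences, with no new data or participants. The drawback is that secondary and subjective results can no longer be called significant on p<0.05 alone.
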